8.4 Pharmacokinetics

8.4.1 Collection of Samples

Blood samples of approximately 2 mL and pooled urine will be collected for measurement of plasma and urine concentrations of CS-1103; respectively, at times as specified in SoA ([Section 1.3](#)) and [Table 2](#) during treatment. The timing of sampling may be altered during the course of the study based on newly available data (e.g., to obtain data closer to the time of peak plasma concentrations) to optimize the PK sample collection schedule for PK parameter calculations. Up to 2 additional blood collections may be added, pooled urine collections may be extended, and discharge may be delayed for up to 8 hours to optimize PK assessment without preparation of an amendment. The timing of PK (both plasma and urine) may be adjusted based on emerging data. In case that CS-1103 half-life is less than 4 hours, PK sampling may be discontinued at a time earlier than 48 hours.

Blood samples will be taken either by direct venipuncture or an indwelling cannula inserted in a forearm vein. On the day of CS-1103 administration, samples should be collected in the contralateral (opposite) arm from the one being used for drug infusion. The actual date and time (24-hour clock time) of each sample will be recorded. Samples will be used to evaluate the PK of CS-1103-01. Each plasma sample will be divided into 2 aliquots (1 each [primary and a back-up]). Samples collected for analyses of CS-1103 plasma concentration may also be used to evaluate safety or efficacy aspects related to concerns arising during or after the study.

The window for the blood collections is detailed in [Table 2](#).

Urine samples for the determination of CS-1103-01 will be collected over the pooled intervals as specified in [Table 2, Section 1.3](#). The actual start and stop date/time of each pooled urine collection as well as the volume of each pooled collection will be recorded. The site will also document whether the entire voided urine was collected for each interval (and complete void volume was recorded).

Blood and pooled urine samples will be collected, labeled, stored, and shipped as detailed in the Laboratory Manual.

8.4.2 Determination of Drug Concentration

Samples for the determination of CS-1103 in plasma and urine will be analyzed on behalf of the Sponsor using appropriate validated bioanalytical methods. Full details of the bioanalytical methods will be described in a separate Bioanalytical Report. Reported CS-1103 concentrations will reflect the concentrations of the tetrasodium salt.

All samples still within the known stability of the analyte of interest at the time of receipt by the bioanalytical laboratory will be analyzed.

Samples collected from participant who received placebo will not be analyzed.

Remaining plasma and pooled urine samples may be subjected to further analysis by the Sponsor or designee for the purpose of the development of additional bioanalytical assays and/or to investigate the presence of CS-1103 metabolic products, if applicable. Samples collected for analyses of CS-1103 (plasma) concentration may also be used to evaluate safety aspects related to concerns arising during or after the study. The bioanalytical laboratory personnel analyzing the PK samples will be unblinded.

8.4.3 Calculation of Derivation of Pharmacokinetic Variables

Pharmacokinetic parameters will be derived using noncompartmental methods with Phoenix® WinNonlin® Version 8.3 or higher (Certara, L.P. Princeton, New Jersey, United States of America [USA]) and/or SAS® Version 9.4 or higher (SAS Institute, Inc., Cary, North Carolina, USA). Actual elapsed time from start of the IV infusion will be used for the final plasma PK parameter calculations. Nominal time from end of the IV infusion will be used for preliminary PK parameter calculations.

The plasma PK parameters in Table 4 will be determined for CS-1103. A minimum of 3 quantifiable postdose concentrations will be required for all calculations.

Table 6 Plasma Pharmacokinetic Parameters

Pharmacokinetic Parameter	Definition
C_{\max}	Maximum concentration, obtained directly from the observed concentration versus time data
C_{EOI}	Concentration at the end of the 10-minute IV infusion
t_{\max}	Time to C_{\max}
$AUC_{(0-\infty)}$	Area under the plasma concentration-time curve from time zero extrapolated to infinity, calculated by linear up/log down trapezoidal summation
$AUC_{(0-\text{last})}$	Area under the plasma concentration-time curve from time zero to the time of the last quantifiable concentration, calculated by linear up/log down trapezoidal summation
CL	Systemic clearance

V_z	Volume of distribution
V_{ss}	Steady-state volume of distribution
$t_{1/2}$	Half-life; a minimum of 3 points will be used for estimation
λ_z	Elimination rate constant

Abbreviation: IV = intravenous.

Note: No dose correction for the sodium salt will be required for dose-dependent parameters, as both CS-1103 dose and plasma concentrations will be based on the weight of the tetrasodium salt.

For this study, an extrapolation of 30% will be considered acceptable for considering $AUC_{(0-\infty)}$ sufficiently well defined. Dose normalized exposure will also be determined. Additional plasma parameters may be calculated if deemed appropriate. Further details with respect to the PK analysis will be provided in the statistical analysis plan (SAP).

Any preliminary plasma PK result for use by the SRC will be reported in a manner that maintains blinding of the treatment the participants have received unless otherwise requested by the SRC. The urine PK parameters in Table 5 will be determined for CS-1103.

Table 7 Urine Pharmacokinetic Parameters

Pharmacokinetic Parameter	Definition
$A_{e(t1-t2)}$	By-interval amount excreted in urine during the pooled collection interval from t_1 to t_2
$A_{e(0-last)}$	Cumulative amount excreted in urine during the pooled collection intervals
$f_{e(t1-t2)}$	By-interval fraction of dose (reported as percent) excreted in urine during the pooled collection interval from t_1 to t_2
$f_{e(0-last)}$	Cumulative fraction of dose (reported as percent) excreted in urine during the pooled collection intervals
CL_r	Renal clearance calculated as $A_{e(0-last)}/AUC_{(0-last)}$

Note: No dose correction for the sodium salt will be required for dose-dependent parameters, as both CS-1103 dose and plasma concentrations will be based on the weight of the tetrasodium salt.

Additional urine parameters may be calculated if deemed appropriate. Further details will be provided in the SAP.

Any changes in the timing or addition of time points for any planned study assessments must be documented and approved by the relevant study team member and then archived in the Sponsor and study site study files but will not constitute a protocol amendment. The IRB will be informed of any safety issues that require alteration of the safety monitoring scheme or amendment of the ICF.

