- l. On Day 1, ASQ will be completed predose (within 60 minutes prior to dosing) and approximately 10 minutes (+15 minutes), 1 hour (+15 minutes), and 2 hours (+15 minutes) postdose. This assessment will be performed after completion of all other simultaneously scheduled procedures to avoid interference with scheduled vital sign, ECG, and PK evaluation (see [Section 8.2.4](#)).
- m. All SAEs will be collected from the signing of the ICF until the last study visit at the timepoints specified in the SoA. All AEs will be collected from the start of study treatment until the last study visit at the timepoints specified in the SoA.
- n. Study Treatment will be administered on Day 1 in the morning after at least a 10 hour overnight fast with an approximately 4 hour fast following dose administration. Note: All scheduled postdose assessments listed in [Table 1](#) and [Table 2](#) are relative to the start of the IV infusion.
- o. PK blood and urine collection timepoints (see [Table 2](#)).

Table 4 Detailed Schedule of PK, Urine, dECG, Safety ECG, ASQ, Injection Site Assessment and Vital Signs During Single IV Administration Days -1 to Day 3

Day	Time Relative to IV Infusion Dose (T=0) ^a and PK windows	Time relative to End of Infusion ^b (EOI)	PK Blood ^b	Urine ^c	dECG ^d and Safety ECG ^e (triplicates)	Vital Signs ^f	ASQ ^g	Injection Site Assessment ^h
Admission/ Day -1	4 hour Holter*				X^{d,e} (4 hour Holter)	X^f	X	
Day 1	Predose (within 60 minutes of dose)	Predose	X (Within 60 mins of start of infusion)		-12 to 0 hr (±15 min)	X^{d,e} (Holter to start approx. 60 mins before start of infusion)	X (within 60 mins of start of infusion)	X (within 60 mins of start of infusion)
		5 minutes into Infusion				X^j (±2.5 min)		
	End of IV infusion (+1 minute)	At End of Infusion (EOI)	Xⁱ (+1 min)			X^j (1 to 4 min post EOI)		X (+15 min)
	15 min (+1 minutes)	5 minutes	Xⁱ (+1 min)					
	20 min (+1 minutes)	10 minutes	Xⁱ (±1 min)					
	30 min (+2 minutes)	20 minutes	Xⁱ (±2 min)					
	40 min (+2 minutes)	30 minutes	Xⁱ (±2 min)					
	50 min (+4 minutes)	40 minutes	Xⁱ (±4 min)					
	1 hr, 10 minutes (+4 minutes)	1 hr	Xⁱ (±4 min)					
	1 hour, 40 minutes (+10 minutes)	1.5 hr	Xⁱ (±10 min)					
	2 hr, 10 minutes (+10 minutes)	2 hr	Xⁱ (±10 min)					
	2 hr, 40 minutes (+10 minutes)	2.5 hr	Xⁱ (±10 min)					
	2 hr, 10 minutes (+10 minutes)	3 hr	Xⁱ (±10 min)		2 to 4 hr (±15 min)	X^e (±10 min)	X (±10 min)	X (+15 min)
	4 hr (+15 minutes)	4 hr	X (±15 min)					X (+15 min)

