	5 hr (+15 minutes)	5 hr			4 to 6 hr (±15 min)			X (+15 min)
	6 hr (+15 minutes)	6 hr	X (±15 min)			X^e (±10 min)	X (±10 min)	X (+15 min)
	8 hr (+15 minutes)	8 hr	X (±15 min)		6 to 12 hr (±15 min)	X^e (±10 min)	X (±10 min)	
	12 hr (+15 minutes)	12 hr	X (±15 min)					
Day 2	24 hr (+30 minutes)	24 hr	X (±30 min)	12 to 24 hr (±15 min)	X^{d,e} (Holter to end after 24-hr)	X (±10 min)		X (+12 hr)
	36 hr (+30 minutes)	36 hr	X (±30 min)	24 to 36 hr (±15 min)		X (±10 min)		
Day 3	48 hr (+30 minutes)	48 hr	X (±30 min)	36 to 48 hr (±15 min)	X^e (±10 min)	X (±10 min)		X (any time prior to discharge)

Abbreviations: ASQ: Anxiety Symptoms Questionnaire; CRU = clinical research unit; dECG: Digital electrocardiogram; EOI = end of infusion; hr = hour; IV = intravenous; min = minutes; PK: pharmacokinetics; (T=0) = Time equals 0.

* Continuous Holter performed during the day of admission

- a. All predose procedures and PK blood samples may be taken up to 60 minutes prior to start of the 10 minute IV infusion on Day 1. All postdose procedures and PK blood samples will be collected relative to the end of the IV infusion unless otherwise indicated or there is a significant extension of the infusion duration (see footnote ^b below).
- b. The following windows will be allowable for PK samples: a ±1 minute window will be allowed for samples taken up to and including 10 minutes postdose, a ±2 minute window will be allowed for samples at 20 and 30 minutes postdose, a ±4 minute window will be allowed for samples at 40 minutes, 50 minutes, and 1 hour postdose, a ±10 minute window for samples taken between 1.5 hours and 3 hours postdose; a ±15 minute window is acceptable for samples taken at >3 hours postdose, and a ±30 minute window is acceptable for samples taken at >12 hours postdose.
- c. A small amount of urine will be removed at each interval for urinalysis. Removal of urine will occur after the volume of the pooled urine has been recorded.
- d. ECGs to be extracted from the continuous Holter on Days 1 and 2 as listed in [Table 2](#) and will be time-matched with PK sample collections from predose to 24-hour postdose. Digital ECG assessments will be extracted at a time prior to the PK sample collection. Participants will remain in supine position for at least 5 minutes before each of the planned ECG extraction.

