- e. Scheduled safety ECG by site for in-time evaluation of ECGs. Timepoints will be from the start of the triplicate assessment as indicated. Single ECG will be collected at the 10 and 30 minutes post EOI timepoints.
- f. Vital signs can be taken any time prior to randomization on Admission/Day -1.
- g. On Day 1, ASQ will be completed predose (within 60 minutes prior to dosing) and approximately 10 minutes (+15 minutes), 1 hour (+15 minutes), and 2 hours (+15 minutes) postdose. This assessment will be performed after completion of all other simultaneously scheduled procedures to avoid interference with scheduled vital sign, ECG, and PK evaluation (see [Section 8.2.4](#)).
- h. On Day 1, the injection site will be evaluated prior to study treatment administration and again immediately after study treatment administration, in approximately hourly (+15 minutes) intervals for up to 6 hours postdose. Injection site assessment also occurs any time on Day 2, and any time prior to discharge from the CRU on Day 3 (see [Section 8.2.1.1](#) for details on the 4 point scale injection site assessment).
- i. If the duration of the short 10 minute infusion exceeds 15 minutes, or an interruption occurs that exceeds the duration of infusion to more than 15 minutes, for PK blood collection (postdose) up and including 3 hours, every effort should be made to follow the time relative to the end of infusion.
- j. Blood pressure measurements for 5 minutes post start of infusion, at EOI, and 20 minute post EOI timepoints will be single readings.

The timing of PK (both plasma and urine), safety ECG, and vital sign assessments may be adjusted based on emerging data. Furthermore, in case that CS-1103 half-life is less than 4 hours, Holter recording may be discontinued at a time earlier than 24 hours post IV infusion. Furthermore, up to 2 additional blood collections may be added on Day 1, Day 2, or Day 3; pooled urine collections may be extended, and discharge may be delayed for up to 8 hours to optimize PK assessment without preparation of an amendment.

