4.6 Study Stopping Criteria

4.6.1 Criteria for Stopping Dose Escalation

Dose escalation will be stopped if any of the following study stopping rules are met:

- One or more participants who received CS-1103 report a serious adverse events (SAEs) considered at least possibly related to the study treatment
- Two or more participants who received CS-1103 experience a moderate AE in the same organ system that are at least possibly related to the study treatment
- One or more participants who received CS-1103 fulfill Hy's law defined as alanine aminotransferase (ALT) or aspartate aminotransferase (AST)] $>3 \times$ the upper limit of normal (ULN) and total bilirubin $>2 \times$ ULN in the absence of significant increase ($>2 \times$ ULN) in alkaline phosphatase (ALP) and in the absence of an alternative diagnosis that explains the increase in total bilirubin, to be assessed from the first administration of study treatment up to and including follow-up/EOS Visit. The event must be considered at least possibly related to study treatment
- Two or more participants, who receive CS-1103, have QTc prolongation defined as QT corrected for heart rate by Fridericia's formula (QTcF) >500 msec, or an increase of QTcF >60 msec above baseline to a value >480 msec on the 12-lead ECG, confirmed (persistent for >5 min) on a repeat 12-lead ECG.
- Any other event in CS-1103-treated participants occurs and is deemed by the SRC to pose an unacceptable risk to participants
- Any participant exceeds predicted exposures equivalent to exposure limits [REDACTED]; AUC_(0-last) (456 $\mu\text{g}\cdot\text{h}/\text{mL}$). If the predefined exposure limits are reached and there are no safety or tolerability concerns, a lower dose may be investigated. If any of these criteria are met, the SRC will stop further dose escalation. The SRC will determine whether a lower dose should be tested or whether the study should be terminated

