9.4 Interim Analysis

No formal interim analysis is planned. Preliminary PK parameters will be calculated using available quality-controlled CS-1103 concentrations and scheduled sampling times to support dose escalation decisions, as applicable.

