15.2. Pharmacokinetic Parameters

For PK parameter calculations, predose samples that are BLQ or missing will be assigned a numerical value of zero. Any anomalous concentration values observed at predose will be identified in the study report and used for the computation of PK parameters. Pharmacokinetic parameters will be computed if the anomalous concentration is not greater than 5% of the observed maximum concentration (C_{max}). If the anomalous concentration is greater than 5%

of C_{max} , the PK parameters for the given subject will be calculated and reported in the listing, but excluded from statistical summaries and analyses.

Any other BLQ concentrations will be assigned a value of zero if they precede quantifiable samples in the initial portion of the profile. A BLQ value that occurs between quantifiable data points, especially prior to C_{max} , will be evaluated to determine if an assigned concentration of zero makes sense, or if exclusion of the data is warranted. Following C_{max} , BLQ values embedded between 2 quantifiable data points will be treated as missing when calculating PK parameters. If a BLQ value occurs at the end of the collection interval (after the last quantifiable concentration), it will be set to zero. If consecutive BLQ concentrations are followed by quantifiable concentrations in the terminal portion of the concentration curve, these quantified values will be excluded from the PK analysis by setting them to missing, unless otherwise warranted by the concentration-time profile.

The following plasma PK parameters will be estimated for CS-1103 by non-compartmental methods using actual elapsed time from the end of infusion. A minimum of 3 quantifiable postdose concentrations will be required for calculation of PK parameters.

C_{max} Maximum concentration, obtained directly from the observed concentration versus time data

C_{EOI} Concentration at the end of the 10-minute IV infusion

t_{max} Time to C_{max}

[figure not shown]
$AUC_{(0-inf)}$ Area under the plasma concentration-time curve from time zero (end of the 10-minute IV infusion) extrapolated to infinity, calculated by linear up/log down trapezoidal summation

$AUC_{(0-last)}$ Area under the plasma concentration-time curve from time zero to the time of the last quantifiable concentration, calculated by linear up/log down trapezoidal summation

CL Systemic clearance, calculated as dose divided by $AUC_{(0-inf)}$

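### Preliminary PK for escalation is timed from the end of infusion and final PK from the start, so the AUC set against the 456 limit has no settled time origin and may read about 5-8% low (minor)

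*Protocol*

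**What the plan says.** Protocol 8.4.3 gives two clocks in adjacent sentences. Final plasma parameters use actual elapsed time from the start of the infusion. For the preliminary ones, "Nominal time from end of the IV infusion will be used for preliminary PK parameter calculations". AUC(0-last) is defined in the same section from time zero to the last quantifiable concentration by linear-up/log-down trapezoids.

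The preliminary results matter because Protocol 9.4 says: "Preliminary PK parameters will be calculated using available quality-controlled CS-1103 concentrations and scheduled sampling times to support dose escalation decisions". SAP 4.1 says the same, and Protocol 4.5 and 10.1.7.1 make SRC review of PK a condition of escalation. Protocol 4.6.1 stops escalation if "Any participant exceeds predicted exposures equivalent to exposure limits". The limit's derivation is redacted, but AUC(0-last) 456 µg·h/mL is visible.

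Other text on the time origin is mixed:

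- Protocol 1.3, Table 1 note n: scheduled postdose assessments "are relative to the start of the IV infusion". Table 2 also has a column that sets T=0 at the infusion dose.
- Protocol 1.3, Table 2 note a: "All postdose procedures and PK blood samples will be collected relative to the end of the IV infusion unless otherwise indicated".
- Table 2 note i: "If the duration of the short 10 minute infusion exceeds 15 minutes", PK sampling through 3 h should follow time from end of infusion.
- SAP 15.2 defines AUC(0-inf) "from time zero (end of the 10-minute IV infusion) extrapolated to infinity" and puts all plasma parameters on actual time from end of infusion. This contradicts Protocol 8.4.3 for final PK. Its AUC(0-last) entry does not say when time zero is.

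**The concern.** A trapezoidal AUC from time zero counts only what lies after time zero. If preliminary time zero is the end of infusion, the rising limb during the infusion is left out. The drug is expected to have a short half-life, so ten minutes of infusion is not a negligible share of total exposure.

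The number affected is one that the SRC may set against a per-participant exposure limit in a first-in-human study. For the same participant, the SRC's AUC and the final AUC under the protocol could differ through timing convention alone. Protocol 9.4 and SAP 4.1 refer only to scheduled sampling times, and the schedule carries both clocks, so neither settles the matter.

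**Working it through.** The documents give no figure for this effect, so there is none to reproduce.

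**Inputs from the documents.** C0 340 µg/mL and AUC(0-last) 318 µg·h/mL at 40 mg/kg (note to Protocol 4.5); infusion 10 min (Protocol 6.1); limit 456 (Protocol 4.6.1); Cohort 4 dose 26.7 mg/kg with 6 active participants (Protocol 4.1); sampling times from Table 2.

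**Assumptions.** Kinetic model, lognormal AUC, between-participant CVs of 20, 30 and 40%, and 456 being a full AUC from start of dosing.

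**1. Share of area lost, one compartment.** k = 340/318 = 1.069 per h, so t½ = ln 2/k = 0.648 h. With infusion time T, the omitted share is 1 - (1 - e^(-kT))/(kT).

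- T = 10 min: kT = 0.1782 and e^(-kT) = 0.8368, so the share is 1 - 0.1632/0.1782 = 8.4%.
- T = 15 min: kT = 0.2673 and e^(-kT) = 0.7654, so the share is 1 - 0.2346/0.2673 = 12.2%.
- T = 10 min with half-lives of 1, 2 and 4 h: 5.6%, 2.8% and 1.4%.

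**2. The same by linear-up/log-down on the Table 2 times** (concentrations of 0.01 µg/mL or less dropped):

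| Infusion | AUC from start | Time zero at end of infusion | Start kept at -10 min |
|---|---|---|---|
| 10 min | 317.2 | 291.2 (8.2% low) | 317.2 (0.0%) |
| 15 min | 316.3 | 279.0 (11.8% low) | 303.9 (3.9% low) |

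At 10 min the difference is the rising-limb triangle: 311.4 × (1/6)/2 = 26.0 µg·h/mL.

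**3. Two-compartment profiles held to C0 340 and AUC 318** (fast half-life 0.08-0.3 h, slow half-life 0.8-3 h, 276 parameter sets). With time zero at end of infusion, the reading is 5.5-8.0% low at 10 min and 7.0-11.5% low at 15 min. With the start kept at -10 min, it is 0.0% and 2.3-3.8% low. A separate set of bi-exponential profiles gave 5.3-8.1% at 10 min. Hence about 5-8%.

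**4. What 456 then means.** A reading of 456 that is low by a fraction b corresponds to a start-based AUC of 456/(1 - b): 482.5 at b = 0.055 and 496.7 at b = 0.082.

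**5. Missed stops.** The last escalation the rule can stop is Cohort 4 to Cohort 5. Projected Cohort 4 AUC = 318 × 26.7/40 = 212. With F the lognormal distribution function (geometric mean 212, log-SD = √ln(1 + CV²)), P(missed stop) = F(456/(1 - b))^6 - F(456)^6.

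| CV | Rule should fire | Missed, b = 0.055 to 0.082 | Missed, b = 0.028 | Missed, b = 0.014 |
|---|---|---|---|---|
| 20% | 0.03% | 0.02-0.03% | 0.02% | 0.01% |
| 30% | 2.7% | 1.2-1.6% | 0.7% | 0.4% |
| 40% | 13.3% | 3.8-5.4% | 2.1% | 1.1% |

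At CV 30% and b = 0.082: 0.9981^6 - 0.9954^6 = 0.989 - 0.973 = 1.6%. A review may proceed on 6 of 8 participants, so only 4 may be active. The missed-stop figures are then 0.02%, 0.8-1.1% and 2.7-3.8%.

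**The case against.** The strongest reply is that the documents do not require time zero at the end of infusion for this AUC. The SAP attaches that definition to AUC(0-inf) only. Table 2 labels the dose T=0 and places the sample 5 minutes after end of infusion at 15 min. SAP 15.2 also sets predose values below quantitation to zero for parameter calculations, which suggests a profile that begins before the infusion ends. If the start is kept at -10 min, the error for a 10-minute infusion is zero. This stands: the 5-8% is conditional, and what remains is that the visible text does not choose between the two readings.

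A reader might infer that the SRC's AUC always errs on the unsafe side. The documents do not support this. The derivation of 456 is redacted, and the protocol's abbreviation list defines animal C0 by extrapolation to end of injection. If 456 is on that basis, an AUC from end of infusion is the matching comparator.

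A reader might also take the rule's predicted exposures to mean Cohort 4 AUC scaled to 40 mg/kg. The missed-stop figures would then be 8.8-17.3% over the same CVs, ignoring the 3000 mg cap. Protocol 4.6.1 does not say that the comparison is made this way.

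Two further replies have weight. The SRC charter, which is not available here, may fix the convention. And timing from the end of infusion has a purpose, because it places samples correctly after a prolonged infusion. The fix therefore has to keep an adjustment for recorded duration.

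**Conclusion.** The inconsistency within Protocol 8.4.3 is real. Read literally, it lowers preliminary AUC(0-last) by about 5-8% at the protocol's 40 mg/kg projection, or by 2.8% and 1.4% at half-lives of 2 h and 4 h. Under the other reading, a 10-minute infusion is unbiased and a 15-minute one reads 2-4% low.

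The direction is non-conservative only if 456 is an AUC from start of dosing, which cannot be confirmed. With observed AUC compared with 456, the effect on planned escalation is small: a missed stop at Cohort 4 in about 0.02% to 5% of trials, on CVs that are not from the documents. Severity is minor. It is still worth correcting, because a numeric stopping limit needs a defined measurement.

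**What to change.** 1. **Protocol 8.4.3:** compute preliminary PK on nominal time from the start of infusion, with concentration 0 at time 0 and the end-of-infusion sample at 10 min. If the infusion was prolonged or interrupted, place that sample at the recorded duration, and samples through 3 h at that duration plus their nominal time after end of infusion.
2. **Protocol 9.4 and SAP 4.1:** say that scheduled sampling times are counted from the start of infusion, with the same adjustment.
3. **SAP 15.2:** change the end-of-infusion clock and the AUC(0-inf) time-zero definition to start of infusion, as Protocol 8.4.3 requires for final PK. Without this, moving only the preliminary clock would create a new mismatch with the SAP's final parameters.
4. **Protocol 4.6.1:** state the time origin of 456. If it is on an end-of-injection basis, either compare it with an AUC on that basis or re-express 456 from the start of infusion.

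The cost is wording in five places. No new data are needed, because Protocol 6.4 already records infusion start, end and interruption times. The start-of-infusion method was itself within 0.1-1.2% of the true AUC for a 10-minute infusion in the profiles above.
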